6.3 Recruitment and Retention

Subjects will be recruited from the Investigator's clinical dermatology practice. The investigator may also recruit subjects using Ethics Committee approved recruitment materials.

6.4 Withdrawal or Termination

6.4.1 Subject Withdrawal

Participation in the study is strictly voluntary. A subject has the right to withdraw from the study at any time for any reason and is under no obligation to disclose the reason. If a subject withdraws, the Investigator and Sponsor are to be informed immediately and the withdrawal noted on the Case Report Form. Subjects may be replaced at the discretion of the Investigator and/or Sponsor only if both are in agreement.

The Investigator has the right to terminate participation of a subject at any time for any of the following:

- Use of non-permitted concomitant medication
- Lack of subject compliance
- Protocol violation
- Disease progression
- Any perceived safety risks

6.4.2 Study Discontinuation

Study discontinuation is at the discretion of the Sponsor or the Investigator in any of, but not limited to, the following events:

- Occurrence of unusual AEs in terms of their nature, severity, causality, duration, or unexpected incidence.
- Medical or ethical reasons affecting the continued performance of the study.
- Difficulties in the recruitment of the subjects.

6.4.3 Stopping Rules

The sponsor (Medical Director/Chief Medical Officer) will halt the study for a review of the safety data if there are safety concerns noted for any reason and if one or more subjects experience two AE's assessed as a Grade 3 (severe) or higher, of the same type that is considered possibly, probably or definitely related to the IP.

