Study Duration Study Population	 Microbiological samples will be collected from the designated TV locations on the chest and back (see Table 3 in section 6.6.3). Each of the two application areas will comprise of an area of approximately 100 cm² which is approximately equivalent to the area of the palm of the hand. At baseline prior to IP, vehicle gel, or aqueous gel application and then on study days 5 and 14, samples for microbiologic evaluation will be collected from designated two anatomic locations. Clinical evaluations of each treated TV area will be scored for disease severity by grading the scaling, erythema, pruritus, and dyspigmentation (hypo or hyperpigmentation) as none, mild, moderate, or severe. In addition, local tolerability will be evaluated by grading signs and symptoms (pain/burning/stinging, edema, scabbing/crusting). In the event of early termination from the study, the Day 14/final visit study procedures will be performed prior to termination, if possible. Approximately 3-4 months from enrollment of the first subject until the last subject's final study visit. 	
Number of Subjects	with TV on the trunk (chest and back). Approximately 22 subjects to be enrolled into 4 Cohorts – with approximately 4 or 6 subjects per cohort	
Number of Clinical Sites (Study Centers):	One. Additional clinical sites may be activated, if necessary.	
Inclusion Criteria	 Subjects must meet all of the following criteria to be included in the study: 1. Ability to understand, agree to and sign the study Informed Consent Form (ICF). If the subject is unable to provide consent him/herself, the subject's legally acceptable representative may provide written consent. 2. Male or Female Subjects of any race 18 - 65 years of age. 3. Subjects with a clinical diagnosis of Tinea versicolor (TV is a common benign superficial cutaneous fungal infection usually characterized by hypopigmented or 	

	 hyperpigmented macules and patches on the chest and back). 4. A positive potassium hydroxide (KOH) examination consistent with Malassezia prior to the treatment period done at the clinical site. 5. Agree to not use soap and water on the chest and back for at least 12 hours before the study visits for Baseline/Day 1, Day 5, and Day 14, and follow all study instructions for use of soap and water on the chest and back during participation in the study.

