For each of the three DBI-002 probiotic cohorts, the single-treatment subjects (approximately 2) will be enrolled first. After every single-treatment subject has completed the Day 5 visit, local tolerability and adverse events (AEs) will be assessed. If there are no safety signals, enrollment of the cohort's multiple treatment subjects (approximately 4) will begin. After every multiple treatment subject has completed the Day 14 visit, local tolerability and adverse events (AEs) will be assessed. If there are no safety signals, enrollment of the next cohort will begin. Cohort 1 must be completed before enrolling Cohort 2. Cohort 2 must be completed before enrolling Cohort 3. If there are safety signals specific to local tolerability and AEs from either of the first two cohorts, the following dose escalating cohort may be not be enrolled if the Investigator and sponsor are in agreement.

Cohort 4 subjects will receive multiple treatments, Enrollment of Cohort 4 is independent of the three probiotic cohorts.

Study Flowchart

Visit 0 (may be combined with Visit 1): Screening and enrollment visit, KOH test of TV-affected chest and back skin locations

Visit 1: Baseline visit, Urine pregnancy test as applicable, clinical grading of signs and symptoms of TV, randomization of IP or aqueous gel to chest and back, scrub samples and samples for bacterial culture of IP and vehicle gel TV-affected anatomical locations prior to applications, application of IP and vehicle gel, adverse event recording

Visit 2: Clinical grading of signs and symptoms of TV, scrub samples and samples for bacterial culture of IP and aqueous gel TV-affected anatomical locations, clinical assessment of local tolerability, adverse event recording

Visit 3: Final study visit. Urine pregnancy test as applicable, clinical grading of signs and symptoms of TV, KOH test of TV-affected chest and back skin locations, scrub samples and samples for bacterial culture of IP and aqueous gel TV-affected anatomical locations, adverse event recording, standard-of-care TV treatment may be provided at the discretion of the Investigator

Subjects enrolled to the multiple treatment dose groups:

Visit 0 (may be combined with Visit 1): Screening and enrollment visit, KOH test of TV-affected chest and back skin locations

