6.6.2 Local Tolerability for Areas Affected by TV (application site reaction)

Local tolerability for anatomical locations to which the IP, aqueous gel and vehicle gel are applied will be evaluated based on these signs and symptoms:

Pain/Burning: as reported by the subject as being the greatest intensity they have experienced within the last 24 hours at Baseline or since the last visit at subsequent visits.

0	None	No pain/burning
1	Mild	Slight burning/stinging sensation; not really bothersome
2	Moderate	Definite warm, burning/stinging that is somewhat bothersome
3	Severe	Hot burning/stinging sensation that causes definite discomfort and
		may interrupt daily activities and/or sleep.

Pruritus: as reported by the subject as being the greatest intensity they have experienced within the last 24 hours at Baseline or since the last visit at subsequent visits.

0	None	No pruritus
1	Mild	Slight pruritus, not really bothersome
2	Moderate	Definite pruritus that is somewhat bothersome
3	Severe	Intense pruritus that may interrupt daily activities and/or sleep

Erythema: as assessed by the Investigator

0	None	No erythema present
1	Mild	Slight pink coloration
2	Moderate	Definite redness
3	Severe	Marked erythema, bright red to dusky dark red in color

Edema: as assessed by the Investigator

0	None	No edema
1	Mild	Slight, but definite edema
2	Moderate	Definite edema
3	Severe	Marked edema

Scabbing/Crusting: as assessed by the Investigator

0	None	No scabbing/crusting
1	Mild	Slight, but definite scabbing/crusting
2	Moderate	Definite scabbing/crusting
3	Severe	Marked scabbing/crusting

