8.5 Relationship of Adverse Events to Study Drug

The following classifications should be used when evaluating the relationship of AEs and SAEs to the investigational drug.

- 1. **None**: No relationship between the experience and the administration of study drug; related to other etiologies such as concomitant medications or subject's clinical state.
- 2. Unlikely: The current state of knowledge indicates that a relationship is unlikely.
- 3. **Possibly**: A reaction that follows a plausible temporal sequence from administration of the study drug and follows a known response pattern to the suspected study drug. The reaction might have been produced by the subject's clinical state or other modes of therapy administered to the subject.
- 4. **Probably**: A reaction that follows a plausible temporal sequence from administration of the study drug and follows a known response pattern to the suspected study drug. The reaction cannot be reasonably explained by the known characteristics of the subject's clinical state or other modes of therapy administered to the subject.
- 5. **Definitely**: A reaction that follows a plausible temporal sequence from administration of the study drug and follows a known response pattern to the suspected study drug and can be confirmed with a positive re-challenge test or supporting laboratory data.

Severity:

- 1. Mild: Awareness of sign or symptom, but easily tolerated
- 2. Moderate: Discomfort enough to cause interference with normal daily activities
- 3. Severe: Inability to perform normal daily activities
- 4. Life-threatening: Immediate risk of death from the reaction as it occurred

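### As written, the 6.4.3 halt rule makes a general safety concern insufficient on its own, and the protocol gives two orders for tolerability scoring and dosing on Days 2 to 5

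*Combined protocol and SAP*

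**What the plan says.** Section 6.4.3 (Stopping Rules) has the sponsor halt the study for a review of safety data "if there are safety concerns noted for any reason and if one or more subjects experience two" adverse events "assessed as a Grade 3 (severe) or higher, of the same type that is considered possibly, probably or definitely related to the IP". It cites no severity scale.

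Section 8.5 holds the adverse event severity scale. Level 3 reads "Severe: Inability to perform normal daily activities" and level 4 reads "Life-threatening: Immediate risk of death from the reaction as it occurred". Level 2 (Moderate) already covers discomfort that interferes with daily activities.

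Section 6.6.2 scores five local tolerability items from 0 to 3 at each treated site. Score 3 for pruritus is "Intense pruritus that may interrupt daily activities and/or sleep"; for erythema it is "Marked erythema, bright red to dusky dark red in color".

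On the repeat-dose visits, the Synopsis flowchart and 4.1.1 list test article application and then local tolerability assessment (Visits 2 to 5). The numbered procedures in 6.5.2 list tolerability scoring and then application for the same days.

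Between stages, the Synopsis and 4.1.1 provide a review: "After every multiple treatment subject has completed the Day 14 visit, local tolerability and adverse events (AEs) will be assessed". A similar review follows the single-dose subjects' Day 5 visit.

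**The concern.** 6.4.3 is the only rule in the available text that makes a halt for review mandatory. Its first clause is broad enough to catch anything worrying, but *and if* ties it to a narrow count of two severe, related events of one type. A site or sponsor following the words would have no obligation to pause for a serious concern outside that count.

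Local tolerability is where the gap is easiest to see. It is part of the primary safety endpoint (4.2.1), the product is a live organism, and section 2.1 lists localised infection and cellulitis as possible though unlikely. A related reaction at the highest local score need not be Severe under 8.5, so it may fall outside the count. If the next dose is also applied before the score is taken, a reaction could be recorded only after the skin has been dosed again.

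**Working it through.** No sample size, power or event figure bears on this point. The check compares texts and counts visits.

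**1. The logic of 6.4.3.** Let A be a safety concern for any reason, and B the two-event count.

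| Situation | Halt required: A *and* B (as written) | Halt required: A *or* B |
|---|---|---|
| Neither A nor B | No | No |
| A, not B | No | Yes |
| A and B | Yes | Yes |

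B without A is hardly a real case, since two severe related events of one type are themselves a concern. As written, therefore, A adds nothing and the rule reduces to B. That is a good reason to think *or* was meant. The middle row is where the two readings part. It includes a single life-threatening related event, two Grade 3 related events of different types, and a related local reaction graded below Severe.

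**2. Does B reach a top-score local reaction?** Taking 8.5 as the scale, compare each 6.6.2 score-3 definition with inability to perform normal daily activities.

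| 6.6.2 item | Basis of score 3 | Requires 8.5 Severe? |
|---|---|---|
| Pain/burning | Definite discomfort; interruption of activities or sleep possible | No |
| Pruritus | Interruption of activities or sleep possible | No |
| Erythema | Appearance | No |
| Edema | Appearance | No |
| Scabbing/crusting | Appearance | No |

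Result: 0 of 5. The first two fit 8.5 Moderate; the other three have no functional element. Section 9.2 can turn a clinically significant worsening into an adverse event, but it does not assign a grade. An investigator may still grade a disabling reaction Severe. The finding is only that nothing in the definitions obliges it.

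**3. Visit order on Days 2 to 5.**

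| Source | First | Second |
|---|---|---|
| Synopsis flowchart, Visits 2–4 and 5 | Application | Tolerability assessment |
| 4.1.1, Visits 2–4 and 5 | Application | Tolerability assessment |
| 6.5.2, Days 2–4 (items 2, 3) | Tolerability scoring | Application |
| 6.5.2, Day 5 (items 4, 8) | Tolerability scoring | Application |

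Appendix 1 does not settle it. It splits Day 1 into before and at application, but gives one column for Days 2–4 and one for Day 5.

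**4. Reach.** Each repeat-dose DBI-002 stage has about 4 subjects, with visits on Days 2, 3, 4 and 5.

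- Scored visits: 4 × 4 = 16.
- Scoring first: all 16 scores are available before a dose at the same visit.
- Application first: all 16 doses precede that visit's score. Only the Day 2 to 4 scores, 4 × 3 = 12, are followed by another dose, at the next visit.

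These counts show where the order matters. They do not predict reactions.

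**The case against.** The strongest reply is that nobody would apply the rule literally. Read as two triggers, 6.4.3 already covers a top-score reaction through its general clause. The Investigator may withdraw a subject for any perceived safety risk (6.4.1), and either party may stop the study (6.4.2). Adverse events are monitored continuously, and DBI-002 cohorts are enrolled in sequence with a tolerability review at each step. All of that stands and limits the reach. But 6.4.1 and 6.4.2 are permissive, and the repeat-dose review falls after that group's dosing has ended. None of it makes the mandatory rule say what it probably means.

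On visit order, the Synopsis and 4.1.1 entries are comma-separated summaries, and the numbered steps in 6.5.2 look like the operative text. Rating pain and pruritus since the last visit (6.6.2) also suits scoring before the dose. This makes 6.5.2 the likelier intention, but the conflict appears in two sections and should not be left to inference.

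A reader might infer more than the text supports:

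- *That the severity scale is undeterminable.* 8.5 does not use the word grade, and the Synopsis says "local tolerability will be evaluated by grading signs and symptoms". But 8.5 is the only adverse event severity scale in the available text, it alone has a level above 3, and it stands beside the same causality terms. Citing it would be editorial.
- *That top-score local reactions escape every safeguard.* The discretionary powers and cohort gates reach them.
- *That a 6.6.2 score of 3 should automatically be a Grade 3 event.* A functional threshold for a study-wide halt is a defensible choice.
- *That blinding makes the rule unworkable.* The halt belongs to the sponsor, and 8.5 rates relationship to study drug, which can be judged blind.

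**Conclusion.** The point holds in two parts. First, read literally, 6.4.3 does not require a halt for a serious safety concern unless two related Grade 3 events of the same type also occur. A related top-score local reaction is one such concern, because 0 of 5 top-score definitions entail 8.5 Severe. Second, the protocol conflicts with itself on whether local tolerability is scored before or after application on Days 2 to 5, affecting about 16 doses per repeat-dose DBI-002 stage.

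The size is modest: unclear wording in a mandatory rule and in the timing of a primary safety measure, with discretionary and between-stage safeguards around both. The conclusion assumes that 8.5 is the scale meant in 6.4.3. The opening of section 9, on adverse event recording, was not in the available text, so an instruction there linking local scores to event grades cannot be excluded. Such a link would weaken the local-reaction example. It would not alter the wording of 6.4.3 or the visit-order conflict.

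**What to change.** 1. In 6.4.3, replace *and if* with *or if*, so that the general concern and the event count are separate triggers.
2. Align the Synopsis flowchart and 4.1.1 with 6.5.2, so that local tolerability is scored before each dose on Days 2 to 5.
3. As an editorial clarification, cite the 8.5 severity scale in 6.4.3.

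Optionally, name a related, treatment-emergent worsening to a 6.6.2 score of 3 as an example of a safety concern that prompts sponsor review. This is better than counting it automatically as a Grade 3 event. If it is counted, three limits are needed:

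- Two sites in one subject should not make two events.
- A one-point rise from a moderate baseline should not qualify. Target lesions must be at least moderate on TV grading (6.6.3), and erythema and pruritus are part of that grading.
- Cohort 4 should be handled separately, since neither of its sites receives DBI-002.

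The cost is protocol wording and one fixed visit order, using scores already collected. The downside is slightly more frequent safety reviews; the action is a halt for review, not termination.

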6.5 Study Visits

The study will be conducted with:

- 1. A screening visit (Day -28 to Day 1),
- 2. Baseline visit (Day 1) for evaluation, sampling and treatment may be combined with the screening visit
- 3. Only for subjects enrolled to receive multiple treatment doses: Treatment and evaluation visits (Days 2, 3, 4)
- 4. Evaluation and sampling visit (Day 5), and treatment only for subjects enrolled to receive multiple treatments
- 5. Safety follow-up visit (Day 14)

6.5.1 Screening Visit

Following written informed consent obtained from each subject, the Investigator will determine whether subjects are eligible to participate in the study by performing screening tests and evaluations.

Women of childbearing potential will be tested for pregnancy with a urine pregnancy test. Women who are pregnant or who have a positive pregnancy test will be excluded from the study.

(-28 Day to Day 1) Screening visit:

- 1. Informed consent.
- 2. Record demographics.
- 3. Review of Inclusion/Exclusion Criteria.
- 4. Ensure no use of soap and water on the chest and back within 12 hours before collection of Baseline scrub samples. Schedule the enrolled subject for Day 1 / Baseline visit if soap and water were used on the chest and/or back within 12 hours of the screening visit.
- 5. Women of childbearing potential will be tested for pregnancy with a urine pregnancy test.
- 6. Medical history.
- 7. Concomitant medication.
- 8. Clinical assessment of signs and symptoms of TV.
- 9. KOH test (TV-affected skin locations).

- 10. Record adverse event, if any.
- 11. If screening is not on the same day as all required Day / Baseline visit assessments and skin sampling, schedule an appointment for Day 1 / Baseline visit.

At the Screening visit, continuous monitoring of concomitant medications, therapies and AEs throughout the study period will begin.

6.5.2 All Other Visits

Study visit assessments will be conducted as presented in Appendix 1. The Treatment Period for subjects receiving a single treatment dose is Day/Visit 1. The Treatment Period for subjects receiving multiple treatment doses is from Day/Visit 1 through Day/Visit 5.

Day 1/Baseline visit (before the IP is applied, the following tasks will have been completed):

- 1. Review of Inclusion/Exclusion Criteria.
- 2. Ensure no direct use of soap and water for at least 12 hours on the areas where the samples are to be collected on the chest and back. After sampling and application, instruct the subject not to use soap and water on the chest and back until the morning of the next day.
- 3. Concomitant medications.
- 4. Clinical assessment of signs and symptoms of TV.
- 5. Score the signs and symptoms of local tolerability of the areas affected by TV.
- 6. Collect scrub samples from each of the TV-affected skin locations to be treated with IP, aqueous gel, and vehicle gel.
- 7. After collecting each scrub sample, pat the sampling location dry with wipes.
- 8. Collect samples for bacterial culture of the IP and vehicle gel TV-affected skin locations. Not required for vehicle gel vs. aqueous gel subjects.
- 9. Assigned IP, aqueous gel, and vehicle gel will then be applied to designated locations on both anterior and posterior trunk (chest or back) by investigative site staff. Approximately 0.1-0.2 ml of the IP, vehicle gel, or aqueous gel will be applied to each selected location.
- 10. Record any adverse events.
- 11. Schedule an appointment for Day 5 for subjects receiving a single treatment dose and instruct the subject to not use soap and water on the chest and back for at least 12 hours before the Day 5 visit. Schedule an appointment for the next day for the Day 2 visit for subjects receiving multiple treatment doses.
- 12. Instruct the subject to not wash the treated locations with soap and water on the anterior and posterior trunk (chest or back) from the time of IP, vehicle gel, and aqueous gel application at the Baseline visit until the morning of the next day.

For subjects enrolled to receive multiple treatment doses only:

Day 2 / Visit 2, Day 3 / Visit 3, Day 4 / Visit 4:

- 1. Clinical assessment of signs and symptoms of TV.
- 2. Score the signs and symptoms of local tolerability of the locations affected by TV.
- 3. Application of the IP, aqueous gel. and vehicle gel by investigative site staff to the assigned TV-affected skin locations.
- 4. Record any adverse events.
- 5. For the Day 2 and Day 3 visits, instruct the subject to not wash the treated locations with soap and water until the morning of the next day after IP, vehicle gel, and aqueous gel application. For the Day 4 visit, instruct the subject not to wash the treated locations with soap and water for at least 12 hours before the next day's Day 5 visit.
- 6. Schedule an appointment for the next day's visit.

Detailed instruction for sample collection and processing are in the Study Operation Manual, provided separately.

Day 5 / Visit 5

- 1. Ensure no direct use of soap and water for at least 12 hours on the areas where the scrub samples are to be collected on the chest and back. For subjects receiving multiple treatment doses, instruct the subject not to use soap and water on the chest and back for at least 12 hours after the Day 5 application.
- 2. Concomitant medications.
- 3. Clinical assessment of signs and symptoms of TV.
- 4. Score the signs and symptoms of local tolerability of the areas affected by TV
- 5. Collect scrub samples from each of the TV-affected skin locations treated with IP, vehicle gel, or aqueous gel.
- 6. After collecting each scrub sample, pat the sampling location dry with wipes.
- 7. Collect samples for bacterial culture of the IP and vehicle gel TV-affected skin locations. Not required for vehicle gel vs. aqueous gel subjects.
- 8. If the subject is receiving multiple treatment doses, the assigned IP, vehicle gel, or aqueous gel will then be applied to designated locations on both anterior and posterior trunk (chest or back) by investigative site staff. Approximately 0.1-0.2 ml of the IP, vehicle gel, or aqueous gel will be applied to each selected location.
- 9. Record any adverse events.
- 10. Schedule an appointment for the Day 14 visit.

Detailed instruction for sample collection and processing are in the Study Operation Manual, provided separately.

Day 14 (±2) Follow up visit (no treatment)

- 1. Ensure no direct use of soap and water for at least 12 hours on the areas where the scrub samples are to be collected on the chest and back.
- 2. Women of childbearing potential will be tested for pregnancy with a urine pregnancy test.
- 3. Concomitant medications.
- 4. Clinical assessment of signs and symptoms of TV.
- 5. Score the signs and symptoms of local tolerability of the areas affected by TV.
- 6. Collect scrub samples from each of the TV-affected skin locations that were treated with IP, vehicle gel, and aqueous gel.
- 7. After collecting scrub samples, pat the sampling site dry with wipes.
- 8. Collect samples for bacterial culture of the TV-affected skin locations that were treated with IP and vehicle gel._Not required for vehicle gel vs. aqueous gel subjects.
- 9. KOH test (TV-affected skin locations).
- 10. Record any adverse events.
- 11. Standard-of-care TV treatment may be provided at the discretion of the Investigator

Detailed instruction for sample collection and processing are in the Study Operation Manual, provided separately.

